#### **The clinical trial will:**

- a. Assess aggregate time spent in seven primary clinical states of BD (remitted; subsyndromal depression, mania or mixed state; and syndromal depression, mania or mixed state).
- b. Assess the weekly completion of KIOS-Bipolar and eMoods.
- c. Determine indices of patient satisfaction with the format, ease of use, time required and patient motivation for continuing use of the patient tools both during the trial and following completion.
- d. Determine patient satisfaction with the clinical information on BD illness trajectory and recommendations to facilitate good health and effective interventions. Note that eMoods does not provide this element of information, therefore no comparative data will be feasible for this one objective.
- e. Assess patient scored life function indices (Life Function Questionnaire (LFQ) over the 52 week period of the study.
- f. Assess the relationship between the 8 symptom items in K-B with relevant items rated both by clinicians and as self-assessments by patients at seven time points (week 0, 8, 16, 24, 32, 40 and 52) in the study. These are times at which clinical care visits will routinely occur, and therefore will not add either to extra burden on the participants, or extra contact time with staff. Subjects randomized to eMoods will be similarly scheduled, with the correlations limited to those feasible with the eMoods product. Self-assessments with the 27 item BISS-Self are routinely obtained as part of regular treatment visits.

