**C. Hypotheses:**

a. Patients randomized to KIOS- Bipolar compared with those randomized to eMoods will have a higher proportion of time in remitted status, lower proportion in syndromal status (Manic, depressed, mixed) and higher

LFQ scores.

- b. Persistence with use of KIOS- Bipolar and eMoods will not differ. Persistence is defined as 1) the proportion of subjects who complete weekly scheduled use of the bipolar self-assessment scales and 2) completion of the 52 week self-assessment protocol.
- c. The proportion of on-time completion of assessments will not differ between groups.
- d. Subject satisfaction, assessed by qualitative questionnaires completed by subjects during and principally shortly following completion or discontinuation of the trial, will not differ between groups.
- e. LFQ subscales will be associated with superior outcomes for the KIOS-Bipolar group.
- f. Correlations between scores on items included in KIOS- Bipolar and similar items on the BISS SR and the BISS 42 will be conducted. Strength of association will be higher between KIOS- Bipolar and BISS comparisons than eMoods-BISS comparisons.
- g. Aggregate changes for the KIOS- Bipolar items and corresponding eMoods items will indicate greater proportions of decreased scores for KIOS- Bipolar

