Focus group(s): There will be an addition of one group at approximately Week 8. The group will have 10 participants and the focus of the group will be related to participants experience with mood charting. Recruitment for group 1 will consist of participants who are not currently enrolled in the 52-week comparative study. One half of the group will be participants who have experienced with mood charting and the other half will be participants with no prior mood charting experience. The focus of the first group will consist of the participants experience with mood charts as well as polling the participants on their preferences for logging in, graphs, and other software features.

Additionally, there will be a focus group at approximately Week 16. The focus group will consist of 10 participants who are currently randomized to the KIOS-Bipolar app. The focus of the second group will be related to their experience using the KIOS-Bipolar app along with suggestions for improvements. The participants will be polled on their preferences related to but not limited to logging in, graphs, advice, as well as other KIOS-Bipolar software features.

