#### **ASSESS KIOS-BIPOLAR OR eMOODS:**

- a. At the beginning of the study subjects will be provided preformatted evaluation sheets and will be encouraged to note observations regarding ease/benefits of use, impediments to use, and suggestions for additional features that would enhance the utility of KIOS-Bipolar or eMoods for sustained health.
- b. We will ask the subjects to estimate how completing the KIOS-Bipolar /eMoods assessments contributed to their self-awareness, attitude, and overall sense of satisfaction with their health status.
- c. We will assess the sensitivity of KIOS-Bipolar to identify improving or worsening by comparing the concordance between subject-assessed items with staff -administered BISS items that address similar symptoms.

**Plan of analysis:** The primary aims of the analyses are to investigate patterns of adherence and attrition. The term adherence refers to the extent to which participants follow the weekly completion of KIOS-Bipolar's eight pivotal symptoms of bipolar disorder. Adherence will be measured through such usage indicators as the proportion of weeks completed on time, the proportion completed only with follow-up prompts, and the number of weeks not submitted. Proportions of stable trajectories or improving trajectories are of primary interest. With  $n=90$  subjects (which allows for as many as 30 of the enrolled 120 subjects to have met some criterion for early termination) in the study we will be able to estimate any proportion within 0.10 with 95% confidence. For proportions larger than 0.9 we will be 95% confident we are within 0.06 of the true proportion. For a trajectory neither improving nor degrading there should be a 0.5 proportion

UTHSCSA tracking number: HSC20150321H

of each. For any hypothesis test for a proportion improving or degrading, i.e. not 0.5, we have 0.80 power at two tail significance of 0.05 to detect 0.65 different from 0.5 with n=90 subjects. For subgroups of patients with n=45 we can detect 0.71 different from 0.5 and with n=30 we can detect 0.74 different from 0.5. When comparing proportions of two subgroups of subjects, we will be 95% confident that the difference in proportions of the two subgroups is less than 0.25 for subgroups of n=30 and smaller than 0.20 for subgroups of size 40. If the proportions are larger than 0.9 (i.e. less variable), then we will be 95% confident that the difference in proportions of two subgroups with n=30(45) is less than 0.15 (0.12).

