### ***d. Adequacy of Protection Against Risks***

#### **Recruitment and Informed Consent**

- Participants will be individually recruited from the respective study sites. The methods of this research as well as the Informed Consent Document and all recruiting materials will be approved by the Institutional Review Boards at the UTHSCSA, University of Louisville, and the University of Cincinnati, respectively.
- Study volunteers will have a detailed discussion of the study requirements and procedures with Drs. [name], [name], [name] or the study coordinator at the respective sites. All information regarding the study procedures will be provided to the subjects in understandable layman terms on an IRB approved informed consent form. Participants will receive up to \$600 for participation (Baseline visit, Weeks 8, 16, 24, 32, 40, and 52 at \$10/appointment plus the 52 weekly activities at \$10/self-assessment) for a total of up to \$600. Focus group participants will be compensated for their participation with a \$20 local state voucher.

At the UT Health Science Center, payment for study related procedures will be paid through use of the Mastercard. Compensation will be automatically credited after completion of each study visit. Name, address and date of birth will be shared with a third-party solely for the purposes of compensation processing. This information will only be used for the administration of the compensation (ClinCard) and will be kept strictly confidential.

In addition to the compensation on the card, the participant may also elect to receive study-related messages (text and/or email).

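### The week-16 focus group is drawn from the KIOS-Bipolar arm only, adding an unbalanced contact to a comparison of adherence and satisfaction, with no planned handling; the likely bias is modest and of unknown direction.

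*Combined protocol and SAP*

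**What the plan says.** The focus-group paragraphs, which follow Table 2 and the software description, plan two sessions. The first, at about week 8, uses outsiders: "Recruitment for group 1 will consist of participants who are not currently enrolled in the 52-week comparative study". The second is different: "Additionally, there will be a focus group at approximately Week 16", and "The focus group will consist of 10 participants who are currently randomized to the KIOS-Bipolar app". On its content: "The focus of the second group will be related to their experience using the KIOS-Bipolar app along with suggestions for improvements". Attendees are also polled on features such as login, graphs and advice. The text does not say how the ten are chosen, who runs the session, or whether it comes before or after that visit's forms. No session for eMoods participants appears anywhere.

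Under Recruitment and Informed Consent: "Focus group participants will be compensated for their participation with a \$20 local state voucher".

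The outcomes concerned are compared between arms. Section C (Hypotheses) expects no difference in persistence (b), on-time completion (c) or satisfaction (d). The last begins "Subject satisfaction, assessed by qualitative questionnaires completed by subjects" and goes on to place the questionnaires during the trial but mainly soon after a participant completes or discontinues. The Plan of analysis states: "The primary aims of the analyses are to investigate patterns of adherence and attrition". Table 1 puts the software evaluation form at weeks 16 and 52. Neither the Plan of analysis nor the paragraphs after it mention focus-group attendees.

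**The concern.** Being consulted about an app partway through a trial may change how a person later uses and rates it. Here that can happen in one arm only, and the outcomes it could touch are those the trial compares. For hypotheses of no difference, a small shift in one arm can either create an apparent difference or hide a real one. Because the plan neither flags the attendees nor says how they are selected, a reader of the results could not tell which had happened.

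The protocol already accepts this type of concern. In the software section it answers a criticism that reminders could confound weekly adherence by sending them only after a missed assessment. The one-arm focus group gets no comparable treatment.

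**Working it through.** **Inputs.** From the documents: 120 enrolled (section B); 90 after allowing for 30 early terminations (Plan of analysis); 10 attendees, all KIOS-Bipolar; session at about week 16 of 52. Assumed, because the documents do not give them: 1:1 allocation, so 60 or 45 per arm, and an absolute effect of 0.1, 0.2 or 0.3 in the ten. The 45-per-arm figures also assume that all ten attendees are among the 45.

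**The plan's own precision.** The 95% half-width for a difference of two proportions is 1.96 × √(2p(1−p)/n).

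- n = 45, p = 0.9: 1.96 × √(2 × 0.9 × 0.1/45) = 0.124 (plan: 0.12).
- n = 30, p = 0.9: 0.152 (plan: 0.15). n = 30, p = 0.5: 0.253 (plan: 0.25).
- n = 40, p = 0.5: 0.219, a little above the plan's 0.20. Nothing below depends on it.

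At the arm sizes used here the half-width is 0.107 (p = 0.9) to 0.179 (p = 0.5) for n = 60, and 0.124 to 0.207 for n = 45.

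**Share of the arm.** 10/60 = 16.7%; 10/45 = 22.2%.

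**Shift in the KIOS-Bipolar proportion.** Shift = share × effect. This applies to one-per-person outcomes such as completing 52 weeks. For the proportion of weeks completed, only weeks 17-52 follow the session, so the shift is multiplied by 36/52 = 0.69.

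| Assumed effect in the ten | Per person, n = 60 | Per person, n = 45 | Weekly, n = 60 | Weekly, n = 45 |
|---|---|---|---|---|
| 0.1 | 0.017 | 0.022 | 0.012 | 0.015 |
| 0.2 | 0.033 | 0.044 | 0.023 | 0.031 |
| 0.3 | 0.050 | 0.067 | 0.035 | 0.046 |

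The signs could equally be negative. Every entry is below the smallest half-width for its arm size (0.107 or 0.124).

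The half-widths are for a yes/no outcome per person. A mean of weekly proportions has a standard deviation no larger than √(p(1−p)), so its half-width may be narrower; the documents give no such SD. The largest weekly shifts would equal the half-width only if the between-person SD were as low as 0.035/(1.96 × √(2/60)) = 0.10 or 0.046/(1.96 × √(2/45)) = 0.11.

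**Effect on a nominal 0.05 test.** Rate = Φ(−1.96 + s/SE) + Φ(−1.96 − s/SE), with SE = √(2p(1−p)/n) and s the per-person shift.

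- Smallest case: n = 60, p = 0.5, effect 0.1. s/SE = 0.0167/0.0913 = 0.18; rate 0.054.
- Largest case for an increase that keeps every proportion at or below 1: n = 45, p = 0.7, effect 0.3. s/SE = 0.0667/0.0966 = 0.69; rate 0.106.
- A decrease is not capped in that way. At n = 45, p = 0.9, effect −0.3, s/SE = 0.0667/0.0632 = 1.05; rate 0.18. This is the extreme corner of the assumed range.

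**Would dropping the ten solve it?** Suppose, for illustration, that the session does nothing but attendees are keener people: 0.95 completion against 0.75 in the other 50. The full arm is (10 × 0.95 + 50 × 0.75)/60 = 0.783; without the ten it is 0.75. The false shift of 0.033 equals the bias from a true session effect of 0.2.

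**The case against.** The strongest reply is that this is one session for ten people, with an assumed effect, in a trial where neither arm was ever the bare app. Both arms get a demonstration, reminders after missed assessments, payment per assessment, and sheets inviting comments on ease of use and features from the start. The $20 voucher is about 3% of the stated $600 maximum. eMoods participants have a contact of their own, an optional weekly email to the coordinator. Most of this stands and is why the point is modest. The email option is different in kind, however, and is not a planned offset.

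Several stronger readings are tempting, and the documents do not support them:

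- **That the session favours KIOS-Bipolar.** Inviting suggestions for improvement could lower satisfaction as easily as raise it.
- **That it breaks a promise of no added contact.** Item f of the trial objectives does say "will not add either to extra burden on the participants, or extra contact time with staff", but this describes assessments that coincide with routine care visits. It says nothing about focus groups.
- **That it falls exactly where satisfaction is measured.** Hypothesis d puts the main measurement at the end of participation. The week-16 form is due at about the same time as the session, but the order is not stated.
- **That Hypothesis a (time in remission, LFQ) is affected.** No mechanism is given by which discussing logins, graphs and advice would change clinical state.

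Feedback during the trial also has a purpose, since the abstract describes software refinement running alongside the study. Waiting until week 52 would delay that feedback and would miss people who stop early.

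**Conclusion.** The imbalance is real: ten KIOS-Bipolar participants and no eMoods participants receive an extra mid-trial contact bearing on compared outcomes, and the plan has no handling for it. The bias is modest and of unknown direction. On the stated assumptions (1:1 allocation, effect 0.1 to 0.3, all ten retained in the 45-per-arm case) it is at most 0.067 on a per-person proportion and 0.046 on weekly adherence, below what the trial can resolve between arms. It does not invalidate the randomized comparison. It is worth correcting because the remedy costs almost nothing before the session and cannot be recovered afterwards if attendees are neither flagged nor chosen by a stated rule.

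**What to change.** In the focus-group paragraphs, state that:

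- the session takes place only after each attendee's own week-16 forms, including the software evaluation form, are complete;
- the ten are chosen at random from willing KIOS-Bipolar participants and flagged in the data.

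In the Plan of analysis, state that:

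- all randomized participants stay in the main between-arm comparison;
- a sensitivity comparison of adherence over weeks 1-15, in all randomized participants, is prespecified. It is free of the session but covers early adherence only, not 52-week completion or final satisfaction;
- any analysis without the ten is labelled exploratory. Even with random choice among the willing, it removes willing people from one arm only and so breaks the randomized comparison.

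Where the timing of product feedback allows, draw the group instead from people outside the comparison, as the week-8 group does, or from participants who have finished week 52. That removes the problem altogether.

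Cost: one extra sensitivity analysis and a small scheduling constraint; for the last option, later feedback if week-52 finishers are used.

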#### **ASSESS KIOS-BIPOLAR OR eMOODS:**

- a. At the beginning of the study subjects will be provided preformatted evaluation sheets and will be encouraged to note observations regarding ease/benefits of use, impediments to use, and suggestions for additional features that would enhance the utility of KIOS-Bipolar or eMoods for sustained health.
- b. We will ask the subjects to estimate how completing the KIOS-Bipolar /eMoods assessments contributed to their self-awareness, attitude, and overall sense of satisfaction with their health status.
- c. We will assess the sensitivity of KIOS-Bipolar to identify improving or worsening by comparing the concordance between subject-assessed items with staff -administered BISS items that address similar symptoms.

**Plan of analysis:** The primary aims of the analyses are to investigate patterns of adherence and attrition. The term adherence refers to the extent to which participants follow the weekly completion of KIOS-Bipolar's eight pivotal symptoms of bipolar disorder. Adherence will be measured through such usage indicators as the proportion of weeks completed on time, the proportion completed only with follow-up prompts, and the number of weeks not submitted. Proportions of stable trajectories or improving trajectories are of primary interest. With  $n=90$  subjects (which allows for as many as 30 of the enrolled 120 subjects to have met some criterion for early termination) in the study we will be able to estimate any proportion within 0.10 with 95% confidence. For proportions larger than 0.9 we will be 95% confident we are within 0.06 of the true proportion. For a trajectory neither improving nor degrading there should be a 0.5 proportion

UTHSCSA tracking number: HSC20150321H

of each. For any hypothesis test for a proportion improving or degrading, i.e. not 0.5, we have 0.80 power at two tail significance of 0.05 to detect 0.65 different from 0.5 with n=90 subjects. For subgroups of patients with n=45 we can detect 0.71 different from 0.5 and with n=30 we can detect 0.74 different from 0.5. When comparing proportions of two subgroups of subjects, we will be 95% confident that the difference in proportions of the two subgroups is less than 0.25 for subgroups of n=30 and smaller than 0.20 for subgroups of size 40. If the proportions are larger than 0.9 (i.e. less variable), then we will be 95% confident that the difference in proportions of two subgroups with n=30(45) is less than 0.15 (0.12).

Assumptions needed for each analysis will be examined to assure they are reasonably well met and the conclusions are valid. End of study overall improvement or not for each measure can be analyzed with logistic regression using covariates and predictors of interest. By focusing analyses on proportions and changes in trajectories, each subject will serve as their own control and trends in improved scores, symptoms and behavior may be identified.

Initially, we will also assess the effects of site, ethnicity, and bipolar disorder subtype (BD I, BD II), but none of these factors will be retained in the final model if they are not shown to be significant moderating factors.

The rate of dropout at any given time will be modeled through logistic regression models, with health, socioeconomic, and treatment factors as explanatory variables. *The impact of quality of life on dropout will be assessed similarly.*

**Outcome Measures from KIOS Analytics:** Knowledge Base performance metrics will be computed to measure the effectiveness of the content provided to patients. These metrics take several forms and are based on changes in the symptom scores for all subjects in the field trial (see Phase I Final Report). Changes in the symptom scores provide a global measure of efficacy. Each of these measures can be computed as a function of changes, either over the course of the entire field trial or at each incremental assessment. This latter approach will provide a measure of effectiveness over time. Other KIOS analytic methods will reveal which specific content in the knowledge base needs improvement. Behavioral frequency analysis will show which patient states are entered most frequently. Behavioral transition analysis will show which conditions are precedents to undesirable states.

**Implementation of Clinical Trial Results into Final Product:** The results of the randomized trial will be used to make further refinements to KIOS-Bipolar. The KIOS-generated results will be used to guide changes to the knowledge base. Suggestions about additional features will be considered in development of the commercialization plans.

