**Table 1. Schema for Randomized Clinical Trial**

Week	0	1-7	8	9-15	16	17-51	24, 32, 40	52	RS
MINI-6.0, Demographics/course of illness	X								
K-TABS/eMoods	X	X	X	X	X	X		X	
Life Functioning Questionnaire	X		X		X			X	
BISS-42,	X		X		X		X	X	
BISS Self-Assessment	X		X		X		X	X	X
KIOS NIH Software Evaluation Form					X			X	

The clinician administered scale will be the 42 item Bipolar Inventory of Symptoms Scale (BISS), however comparisons will be limited to the symptom areas represented in both K-B and eMoods, e.g., depression and mania subscales; depression, mania, irritability and anxiety domains. The BISS Self (BISS-S) is a 27item scale covering similar symptoms to the BISS, but answered as yes/no, rather than the 0-4 range of the BISS. The MINI is a structured diagnostic interview providing current and lifetime psychiatric diagnoses, requiring approximately 20 minutes.

g. Estimate the utility of ancillary features of Kios-Bipolar or eMoods. These features include capability to submit to the investigative staff displays of symptom trajectories for the patient's medical record and visual displays of selected aspects of the patient's illness/wellness. No transmission of data to treating clinical staff will occur as component of this study.

h. Assess sensitivity of K-B assessed improvement or worsening by comparison with assessment by BISS-Self and BISS-42.

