**Table 2. BISS Item and Corresponding KIOS-BIPOLAR Questionnaire**

BISS Item	KIOS-BIPOLAR Question
Affective Lability	Have your emotions shifted fairly suddenly at times?
Sadness	Have you felt depressed, sad or down?
Irritability	Have you felt easily irritated, angry or resentful?
Pessimism	Have you been discouraged, pessimistic or felt hopeless?
Anxiousness	Have you felt tense or anxious?
Less Need for Sleep	Were there nights you needed less sleep than usual?
Psychomotor Slowing	Have you felt slowed down?
Energetic	Have you had more energy than usual to do things?

**Software:** Subjects assigned to KIOS-Bipolar will have the app loaded onto their preferred device. The program is available for iPhone and Android devices, and accessible on a pc. The research coordinator will demonstrate the KIOS-Bipolar operation with the subject and ask the subject if he/she has any questions about the procedures of the trial. A phone number and email address will be provided to allow the subject to make contact if any question arises after leaving the clinic. The data entry procedure will take less than 5 minutes per session, with most subjects completing their entries in 2 minutes.

For participants who have been randomized to the eMoods App an additional procedure will occur. After each completed weekly entry on eMoods, the participant will have the option to email the results to the Research Coordinator weekly or postpone sending data until their scheduled research visit.

The subject will be told that an email, text, or push notification reminder will be sent one day after a missed scheduled assessment. The participants phone number will be shared with a third-party (Twilio) solely for the purpose of reminding the participant to complete their questionnaire. This information will only be used for the administration of the push notification and will be kept strictly confidential. The participant will not have the option to opt out of the notification. For participants randomized to KIOS-Bipolar, a text message reminder will be sent one day after a missed scheduled assessment. The participant's phone number will be added to New Patient section in KIOS-Bipolar.

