## RISKS TO HUMAN SUBJECTS

### ***a. Human Subjects Involvement, Characteristics, and Design***

The collaborating sites are the UTHSCSA, the University of Louisville and the University of Cincinnati. Under the direction of [name], Biomedical Development Corporation will create an identical set of study binders containing source documents and case report forms for each of the study sites. Each site will have a designated study coordinator who will be responsible for obtaining, managing and protecting the data. All study materials will be kept under lock and key. The study sites will be monitored throughout the project period by BDC for study compliance, including a preliminary monitoring visit prior to the initiation of the trial to ensure that the study site is adequately equipped and staffed to perform the trial.

The Federal Wide Assurance number for the UTHSCSA is FWA00005928. The Assurance of Compliance number for the UTHSCSA is IRB00000553. The Federal Wide Assurance number for the University of Louisville is FWA00002211. The Federal Wide Assurance number for the University of Cincinnati is 00003152. The Federal Wide Assurance number for Biomedical Development Corporation is FWA0000749.

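### The BISS-42 is the staff-rated check on app scores, but nothing stops its rater from seeing those scores first

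*Combined protocol and SAP*

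**What the plan says.** The staff-rated BISS-42 is the comparator for app scores in several places:

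- Item f under *The clinical trial will* relates the KIOS items, and eMoods items where feasible, to clinician-rated and self-rated items at weeks 0, 8, 16, 24, 32, 40 and 52.
- Item h, below Table 1, reads "Assess sensitivity of K-B assessed improvement or worsening by comparison with assessment by BISS-Self and BISS-42".
- Hypothesis f in section C states: "Strength of association will be higher between KIOS- Bipolar and BISS comparisons than eMoods-BISS comparisons".
- Item c under *ASSESS KIOS-BIPOLAR OR eMOODS* describes "comparing the concordance between subject-assessed items with staff -administered BISS items that address similar symptoms".

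The plan also describes how app data reach research staff. The *Software* text after Table 2 says "For participants who have been randomized to the eMoods App an additional procedure will occur": after each weekly entry, "the participant will have the option to email the results to the Research Coordinator weekly or postpone sending data until their scheduled research visit". Item g below Table 1 lists, for either app, the "capability to submit to the investigative staff displays of symptom trajectories for the patient's medical record". The human-subjects section adds: "Each site will have a designated study coordinator who will be responsible for obtaining, managing and protecting the data".

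The BISS-42 is called clinician-administered in section D and under Table 1, and staff-administered in item c. No individual or role is named as its rater.

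**The concern.** A reference rating is useful as a check on an app score only if it was made without knowledge of that score. If the rater has read the participant's own entries for sadness, irritability or anxiety, the BISS rating of the same symptoms may drift towards them. Part of the observed agreement then comes from the rating procedure and not from the app. This is separate from the overlap in content between the KIOS items and the BISS, and it would remain with perfectly matched items.

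Hypothesis f is the most exposed analysis, because it compares agreement between arms and the one concrete delivery route exists in one arm only. Independent ratings cannot be recovered afterwards, and the plan does not record whether a rater had seen app data.

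**Working it through.** The plan gives no target, precision or power for any concordance or correlation, so there is no figure of its own to reproduce. The check is a comparison of passages, followed by an illustration.

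**1. Is there a safeguard?** The trial is described as open. No passage orders the BISS-42 before app review, masks the rater to app scores or arm, or separates the rater from the recipient of app data. The only limit on data flow, in item g below Table 1, rules out transmission to treating clinical staff. It does not cover research staff.

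**2. Which route affects which analysis?**

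- *Email or visit handover (eMoods only).* This can raise eMoods-BISS agreement. It cannot affect KIOS-BISS agreement or KIOS sensitivity to change.
- *Submitted displays (either app).* This is the only documented route that could raise KIOS concordance and KIOS sensitivity to change. It is described as a capability, with no schedule and no recipient more specific than investigative staff.

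**3. Which visits?** The BISS-42 is scheduled at seven visits. Before week 0 there are no weekly entries to email, so weekly emails can affect at most 7 − 1 = 6 visits. At week 0 only a same-day app entry could be seen, and only if it preceded the rating.

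**4. How large could it be?** Let A be the app score and B the rating an unexposed rater would give, both with unit standard deviation and correlation r. Let an exposed rater record (1 − w)B + wA. Then

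r′ = [w + r(1 − w)] / √[w² + (1 − w)² + 2w(1 − w)r].

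Both r and w are assumptions; the documents give neither. With r = 0.50:

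- w = 0.1: 0.55 / √0.91 = 0.55 / 0.954 = 0.58
- w = 0.2: 0.60 / √0.84 = 0.60 / 0.917 = 0.65
- w = 0.3: 0.65 / √0.79 = 0.65 / 0.889 = 0.73

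Over a range of true correlations:

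| True r (assumed) | w = 0.1 | w = 0.2 | w = 0.3 |
|---|---|---|---|
| 0.30 | 0.40 | 0.50 | 0.61 |
| 0.50 | 0.58 | 0.65 | 0.73 |
| 0.70 | 0.75 | 0.80 | 0.85 |

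If only one arm is exposed and the true correlations are both 0.50, the spurious arm difference is 0.08, 0.15 or 0.23.

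**5. What would a test of hypothesis f do?** The *Plan of analysis* works with 90 subjects. Assuming 1:1 allocation, which the documents do not state, that is 45 per arm. Take one correlation per arm, at one visit. The standard error of the Fisher z difference is √(2/42) = 0.218. The z shifts from r = 0.50 are 0.108, 0.234 and 0.382, or 0.50, 1.07 and 1.75 standard errors. A two-sided 5% test of equal correlations would then reject in about 8%, 19% or 42% of trials. If the exposed arm is eMoods, nearly all of those rejections point towards eMoods.

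**The case against.** The strongest reply is that the central link is undocumented. App data go to the research coordinator, whose stated duties concern data; the BISS-42 is rated by a clinician or staff member who is not identified. Rater and recipient may already be different people. This stands, and it makes the harm conditional. It does not remove the omission, because the plan neither names the rater nor excludes the overlap.

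Three further points stand in part:

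- **Priority.** The *Plan of analysis* names adherence and attrition as its primary aims, with trajectory proportions also of primary interest. App-BISS concordance is not among them. That limits the importance of the point but does not make hypothesis f interpretable.
- **A second comparator exists.** Item h and hypothesis f also use the BISS self-report, which this route does not touch. It shares its informant with the app, so it cannot replace an independent rating.
- **Email is optional.** Participants may hold their data until the visit. However, the visit is when the BISS-42 is due, so the order within the visit still matters.

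A reader might infer that the gap favours the sponsor's product. The documents do not support that: the concrete route is eMoods-only and works against hypothesis f. A reader might also infer that the comparison of time in clinical states (hypothesis a) is affected. Section D lists both the BISS and KIOS as measures of clinical status, but no passage says which instrument assigns the states, so that step is not supported.

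**Conclusion.** The point holds as a design omission with conditional harm. App data can reach research staff before the BISS-42 is rated, and nothing in the plan keeps the rater from seeing them. If the rater has seen them, app-BISS agreement can be inflated. By the email route this raises eMoods-BISS agreement at up to six post-baseline visits. A finding in favour of KIOS would then be conservative in this respect, while a null or reversed finding could not be read cleanly. KIOS concordance and sensitivity to change could be inflated only through submitted displays. The net direction is not determined.

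The illustrated size is an arm difference in correlation of 0.08 to 0.23. It rests on an assumed true correlation of 0.50, equal variances, weights of 0.1 to 0.3 and exposure in one arm only. It shows the mechanism and is not an estimate for this trial. The documents do not show that contamination will occur, that the coordinator is the rater, or that all seven visits are equally exposed.

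**What to change.** Add a short procedural paragraph:

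1. Name the role that rates the BISS-42.
2. At each of the seven visits, complete and lock the BISS-42 before the rater opens or receives that participant's app scores, displays or eMoods handover.
3. At week 0, complete it before the allocation is revealed.
4. Where existing staffing allows, have eMoods emails opened by someone other than the rater. Otherwise, record at each visit, by arm, whether the rater had seen app data before rating, and report concordance by exposure. That report would be descriptive, because participants choose whether to email weekly.

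The cost is the paragraph, possibly one extra field on the visit form, and a small scheduling constraint within the visit. Sample size and visit schedule do not change, and no additional rater is needed.

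The handling of emails between visits has to be settled in the same edit. Visits are 8 weeks apart, and 12 weeks apart between weeks 40 and 52. Section c, *Potential Risks*, commits to conveying evidence of worsening between visits to the psychiatrist or therapist, while item g below Table 1 says that no data go to treating clinical staff. These two passages must be reconciled with each other and with whatever rule is written for opening emails.
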